5.2. Analysis Populations

5.2.1. Intent-to-Treat Population

The intent-to-treat (ITT) population includes all subjects who are randomized to treatment, regardless of whether they received treatment or not.

5.2.2. Modified Intent-to-Treat Population

[figure not shown]
The modified intent-to-treat (mITT) population includes all subjects who have met all eligibility criteria and experienced no major protocol deviations during the study, received at least one dose of study treatment (except for BSC subjects) and had at least one post-randomization treatment response assessment performed. Major protocol deviations leading to exclusion from the mITT population are defined as any of the following:

- Had at least one inclusion/exclusion criteria violation;
- Disease status at screening not confirmed by retrospective central review;
- Initial study treatment given is not the one assigned in randomization;

- Did not have at least one post-randomization efficacy assessment performed;

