#### 9.2.2. Modified Intent-to-Treat Population

The modified intent-to-treat (mITT) population includes all subjects who have met all eligibility criteria and experienced no major protocol deviations during the study, received at least one dose of study treatment and had at least one treatment response assessment performed. This definition will be further clarified and detailed in the final SAP prior to database lock.

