10. EFFICACY ANALYSIS

All efficacy analysis will be performed on the ITT population unless otherwise specified. Key efficacy analyses will also be performed on the mITT population as supportive evidence and to assess the robustness of the efficacy findings. Subjects will be analyzed according to randomized treatment group. Statistical comparisons will be made between AG-221 and CCR overall and by pre-selected CCR therapy whenever applicable.

All statistical tests will be two-sided at the significance level of 0.05, and the corresponding two-sided p-values and two-sided 95% confidence interval (CI) for intended point estimates will be reported, unless specified otherwise.

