10.2. Analysis of Primary Efficacy Endpoint

The primary efficacy endpoint of OS is defined as the time between randomization and death from any cause. Subjects who are alive or whose death status is unknown will be censored at the last date known alive on or before data cutoff date. The OS period in months is calculated as (the earlier of death date/the last date known alive and cutoff date – date of randomization + 1)/30.4375. For subjects who were known to be alive and in the study at data cut-off (were not lost to follow-up, and had not withdrawn consent), the last known-to-be-alive date is set to be the data cut-off date.

The analysis of the primary endpoint will be based on the ITT population. Subjects will be analyzed as they were randomized, regardless of the actual treatment received. The survival distribution of OS will be estimated using Kaplan-Meier (KM) method. The 25th percentile, median and 75th percentile of OS including two-sided 95% CI for each treatment arm will be provided, and their differences with 95% CIs between two arms will be calculated using Kosorok's method. KM curves will be provided by treatment arm in figures.

A stratified log-rank test will provide the pivotal p-value for the comparison of the two survival curves of AG-221 vs. CCR arm overall. Hazard ratio and its two-sided 95% CI will be estimated from a stratified Cox proportional hazards regression model. The stratification factors are:

- Prior intensive therapy for AML: yes versus no
- Primary refractory: yes versus no
- Prior allogeneic HSCT for AML: yes versus no

They are assessed by investigators and captured both in the IVRS system at the time of screening phase and in the CRF. In case the site made a stratification error at the time of screening/randomization, stratification errors are corrected in the CRF. Stratified analysis will use stratification factors taken from the CRF. If data does not converge in the stratified analysis due to small sample size in stratum or if there are less than 40 subjects in a stratum, the stratification factor leads to least subjects will be dropped from the model.

Reasons for censoring (e.g., lost to follow-up, withdrew consent, alive at data cut-off, Discontinuation due to other reasons) will be summarized (n, percent) for the OS endpoint.

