An unstratified log-rank analysis and Cox regression will be considered as supporting analyses. Stratified analyses based on IVRS stratification factors will be included as a sensitivity analysis.

The analyses on the primary endpoint will be repeated for AG-221 versus BSC Only, Azacitidine + BSC, LDAC + BSC, IDAC + BSC individually by pre-selected CCR therapy.

In addition, sensitivity analyses will be done in the following ways:

1. Analysis of OS using mITT population;
2. Censoring subjects at the time of transplantation after study treatments;
3. Censoring subjects at the start date of any subsequent AML therapy;
4. Censoring subjects at the start date of any subsequent therapy for diseases other than AML excluding the use of hydroxyurea;
5. Censoring subjects for subsequent treatment of AG-221 after initial CCRs;
6. Inverse Probability of Censoring Weighted (IPCW) method censoring subjects at off-protocol AG-221;
7. IPCW method censoring subjects at any subsequent AML therapies if applicable;
8. Rank Preserving Structural Failure Time (RPSFT) model adjusting the confounding effect of off-protocol AG-221 if applicable;
9. Regression based imputation method adjusting subsequent AML therapies if applicable.

At the final analysis, the assumption of proportional hazards will be tested using a time-dependent Cox model with categorical variables for survival time (e.g., 0 – 3 months, 3 – 6 months, 6 – 9 months, etc.) and with following covariates:

- Treatment
- Prior intensive therapy for AML (yes, no) from CRF;
- Prior refractory (yes, no) from CRF;
- Prior stem cell transplants for AML (yes, no) from CRF;

If the model does not converge due to small sample size, the covariate leads to least subjects will be dropped from the model. If a stratification factor covariate has less than 40 subjects in one of its levels across treatment groups, then this factor will not be used in stratified analysis; A statistically significant estimation of any of these survival time categories indicates that the proportional hazard assumption is violated. A figure of smoothed hazard function over time will give an instinct idea of hazard trend over time.

If proportional hazard assumption is violated, the following sensitivity analyses will be conducted using ITT population:

1. Restricted mean survival time will be calculated between AG-221 and CCR arms;
2. Piecewise cox regression will provide hazard estimates for every 3 months;

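### mITT membership requires a post-randomization response assessment, so the mITT analyses cannot show robustness to early deaths or to differential non-assessment

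*SAP*

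**What the plan says.** SAP 5.2.2 requires, besides eligibility, dosing and no major deviation, that a subject "had at least one post-randomization treatment response assessment performed". The list of major deviations in the same section repeats this in different words: "Did not have at least one post-randomization efficacy assessment performed". The term efficacy assessment is not defined. BSC subjects are exempt from the dosing condition only.

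Protocol 9.2.2 already contains the condition: the subject "received at least one dose of study treatment and had at least one treatment response assessment performed". It adds that the SAP will clarify and detail the definition.

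Protocol 6.2 ties response assessment to marrow collection. The Table of Events (footnote w) places the first on-treatment marrow in the 7 days before Cycle 2 Day 1, on one schedule for all arms.

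The stated purpose is in SAP 10: "Key efficacy analyses will also be performed on the mITT population as supportive evidence and to assess the robustness of the efficacy findings". SAP 10.2 lists "Analysis of OS using mITT population" as the first OS sensitivity analysis, and SAP 10.3.1 uses mITT for ORR and EFS as well. Protocol 9.6 assigned mITT to the key secondary analyses only. ITT remains primary for OS: "The analysis of the primary endpoint will be based on the ITT population".

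**The concern.** The condition is a post-randomization outcome in an open-label trial, and it overlaps the endpoint. A subject must normally survive about four weeks to meet it. Death is the OS event and one of the EFS events, so the set removes events that a robustness check should register. For ORR, the subjects removed are those whom SAP Appendix 15.5 classes as not evaluable, and they leave the denominator.

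Early mortality matters to this plan. Treatment mortality at 30 and 60 days is a secondary endpoint, and Protocol 7.2.1.3 warns that differentiation syndrome under AG-221 may be fatal if untreated. If the arms differ in the first month, mITT agreement with ITT, or a better mITT result, could be read as reassurance that the analysis cannot give.

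**Working it through.** **Inputs.** Median OS 5.6 months (CCR) and 8 months (AG-221), exponential survival, 158 subjects per arm, 250 deaths, 80% power, two-sided 0.05 (Protocol 9.3, SAP 4.4). Treatment starts 0 to 3 days after randomization (Protocol 3.1.2). The first marrow therefore falls at about Day 22 to 28 of treatment, or up to about Day 31 from randomization, if Cycle 2 is not delayed. A month is 30.4375 days (SAP 15.1.1).

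**1. The plan's own figure.** HR = 5.6/8 = 0.70. The Schoenfeld formula gives 4 × (1.960 + 0.842)² / (ln 0.7)² = 247 deaths. With the planned interim at 163 of 250 deaths, the O'Brien-Fleming-type boundaries come out at one-sided 0.0055 (HR 0.6715) and 0.0233 (HR 0.7775), with power 80.05%. The stated 250 is reproduced.

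**2. Deaths before the first assessment.** P(death by day d) = 1 − exp(−ln 2 × (d/30.4375) / median).

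| Cut-off | CCR | AG-221 | Deaths, both arms | Share of 250 |
|---|---|---|---|---|
| Day 22 | 8.6% (13.5) | 6.1% (9.6) | 23 | 9.2% |
| Day 28 | 10.8% (17.0) | 7.7% (12.1) | 29 | 11.6% |
| Day 31 | 11.8% (18.7) | 8.4% (13.3) | 32 | 12.8% |

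These are upper figures, because a subject with an unscheduled assessment before death stays in. Survivors who are never assessed would be further exclusions; the documents give no rate for them.

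**3. Medians at Day 28.** With constant hazards, survival beyond Day 28 has the same distribution again. Conditioning on it adds 28/30.4375 = 0.92 month: 5.6 + 0.92 = 6.5 and 8.0 + 0.92 = 8.9 months.

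**4. Hazard ratio under the plan's assumptions.** Constant hazards also leave the ratio unchanged after conditioning. A simulation of 400,000 subjects (error about 0.003) gives 0.70 in both ITT and mITT.

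**5. Hazard ratio if the arms differ early.** Assume an AG-221 versus CCR hazard ratio of h before Day 28 and 0.70 afterwards. The values of h are assumptions.

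| h | Excluded CCR / AG-221 | ITT HR | mITT HR |
|---|---|---|---|
| 1.0 | 10.8% / 10.7% | 0.73 | 0.70 |
| 1.5 | 10.9% / 15.7% | 0.78 | 0.70 |
| 2.0 | 10.8% / 20.5% | 0.84 | 0.70 |

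The mITT estimate does not respond to the early effect.

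**6. Hazard ratio if survivors go unassessed.** Assume BSC is 10% to 30% of CCR and 25% to 50% of BSC survivors have no marrow (neither figure is in the documents). If the missing marrows are random, mITT stays at about 0.70. If they are concentrated in short survivors, mITT gives 0.71 to 0.80, which is against AG-221.

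**7. ORR.** If the early deaths are unassessed, dropping them at Day 28 multiplies the observed rate by 1/(1 − 0.108) = 1.12 in CCR and 1/(1 − 0.077) = 1.08 in AG-221.

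**The case against.** The strongest reply is that mITT is supportive only and that, under the proportional hazards on which the trial is designed, the exclusion does not move the hazard ratio. Both points are right. ITT carries the pivotal OS test and the main ORR and EFS analyses. mITT also still checks eligibility violations, disease status not confirmed centrally, and wrong initial treatment. A reader might infer that mITT cannot test robustness at all; that goes too far.

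Second, not every early death is lost. Protocol 6.2 and 6.5.1 allow assessments when clinically indicated, and Protocol 6.2.3 includes a marrow at end of treatment. The undefined efficacy assessment might also be read to include hematologic improvement, which Protocol 6.5.2 bases on transfusion records and central hematology. This stands, and it is why the counts are upper figures.

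Third, a reader might infer that BSC subjects, or control subjects who decline their option, are the likeliest to be removed. The documents do not support this. The marrow schedule is the same for every arm, inclusion criterion 5 requires willingness to receive the pre-selected option, and no BSC share or missing-marrow rate is given.

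Fourth, for EFS the effect is narrower. SAP 10.3.1.2 already censors living subjects without an assessment at randomization in ITT, so mainly the early deaths matter there.

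Fifth, SAP Section 6 summarizes mITT disposition by treatment group and lists exclusion reasons. That shows the size of the loss by arm, but no table by arm and reason is stated.

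**Conclusion.** The concern holds in a limited form. As defined, mITT cannot show robustness to early mortality or to differential non-assessment, although SAP 10 presents it "as supportive evidence and to assess the robustness of the efficacy findings". Up to about 23 to 32 deaths, 9% to 13% of the planned 250, leave the OS mITT analysis. Absolute medians rise by about 0.9 month at a Day 28 cut-off, and unassessed non-responders leave the ORR denominator.

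The counts rest on the plan's exponential medians and on no earlier unscheduled assessment. The divergence between ITT and mITT rests on assumed early hazard ratios or assumed patterns of missing marrow. The direction of bias is not fixed: excess early AG-221 deaths make mITT too favorable to AG-221, while selective loss of short-surviving controls makes it too unfavorable. The primary ITT analysis and type I error are unaffected, so this is a cheap improvement and not a threat to the main result.

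A reader might also infer that Protocol 9.2.2 leaves the definition open. It does not: it sets the assessment condition itself and lets the SAP only clarify and detail it.

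**What to change.** For the OS and EFS mITT analyses, delete the response-assessment condition and the matching efficacy-assessment bullet from SAP 5.2.2. Keep eligibility, central confirmation of disease status and the initial-treatment criterion. Dropping the last would be a trade-off, since it serves as an adherence check.

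For mITT ORR, count unassessed (NE) subjects as non-responders. If a response-evaluable set is wanted, define it separately and label it descriptive.

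In SAP Section 6, add a table of mITT exclusions by arm and reason.

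The cost is SAP text; no new data are needed. The downside is a departure from the condition in Protocol 9.2.2, which must be recorded in SAP Section 13. That section currently lists only the added transfusion-independence analysis.

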5.2.3. Safety Population

The safety population includes all randomized subjects who received at least 1 dose of study treatment. Because BSC only treatment may consist of blood products or antibiotics, etc. administered as needed, subjects who are randomized to the BSC arm option will be included in the safety population if they have had at least 1 safety assessment after randomization. The safety population will be used for all safety analyses and drug exposure. Subjects will be analyzed according to the initial treatment actually received.

6. SUBJECT DISPOSITION

Subject disposition (analysis population allocation, entered, discontinued, along with primary reason for discontinuation) will be summarized using frequency and percent for both treatment and follow-up phases. Enrollment by country and site will also be summarized.

The disposition of subjects will be summarized with counts and percentages. A summary of subject disposition will be presented by treatment group for the following analysis populations:

- ITT population
- mITT population
- Safety population

A listing of reasons for exclusion from the mITT population will be provided. A separate listing will be provided for subjects who were not randomized (screen failures) with reasons for screening failure.

Reasons for treatment discontinuation will be collected on the case report form (CRF) and will be summarized for all randomized subjects with the following categories:

- Death
- Adverse event
- Pregnancy
- Progressive disease
- Withdrawal by subject
- Non-compliance with study drug
- Lost to follow-up
- Study terminated by Sponsor
- Transition to commercially available treatment
- Physician decision
- Disease relapse
- Protocol violation (to be specified on the eCRF)
- Other (to be specified on the eCRF)
- Other: Hematopoietic Stem Cell Transplantation

Reasons for study discontinuation will be collected on the CRF and will be summarized for all randomized subjects and all subjects who enter the follow-up phase with the following categories:

- Screen failure
- Death
- Adverse event
- Pregnancy
- Progressive disease
- Withdrawal by subject
- Lost to follow up
- Study terminated by sponsor
- Transition to commercially available treatment
- Physician decision
- Disease relapse
- Protocol violation (to be specified on the eCRF)
- Other (to be specified on the eCRF)

Additional summaries will be provided for number of subjects per randomization stratum by randomized treatment group, as well as number of subjects by study site.

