### 6.3. Follow-up Phase

All subjects discontinued from study treatment for any reason other than withdrawal of consent for follow-up will continue to have the following assessments in the Follow-up Phase:

[figure not shown]
- AEs, [REDACTED] concomitant medications, concomitant procedures and transfusions for 28 days after the last study treatment or the EOT visit, whichever is longer.

Thereafter, SAEs made known to the investigator at any time that are suspected of being related to study treatment, as described in Section 10.1.

- Transfusions [REDACTED] will continue to be collected until the initiation of the first subsequent AML therapy after discontinuation from study treatment, death, lost to follow-up, withdrawal of consent for further data collection, or the End of Trial, whichever occurs first.
- Bone marrow aspirate and/or biopsy, peripheral blood smear and, if applicable, cytogenetics, available for both local and central review for assessing response or

disease status, every 12 weeks ( $\pm$  28 days) or more frequent if clinically indicated until PD, the initiation of the first subsequent AML therapy after discontinuation of study treatment, death, lost to follow-up, withdrawal of consent for further data collection, or the End of Trial, whichever occurs first.

- Response/disease status and HI will be assessed whenever bone marrow samples are collected for assessing response or disease status (see above)

- Survival follow-up every 4 weeks ( $\pm$  7 days) until death, lost to follow-up, withdrawal of consent for further data collection, or the End of Trial, whichever occurs first. Subsequent AML therapies should be collected at the same schedule as survival follow-up.
- Investigator-assessed response/ disease status to subsequent AML therapies will be collected. Specifically, the best response to a subsequent AML therapy and the first date achieving the best response, and progressive disease/relapse date during or after a respective subsequent AML therapy should be reported.
- Survival follow-up, subsequent AML therapies, and response/ disease status to subsequent AML therapies may be conducted by record review (including public records) and/or telephone contact with the subject, family, or the subject's treating physician.

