### 9.6.1. Primary Efficacy Analysis

The primary efficacy endpoint of OS is defined as the time between randomization and death from any cause. All subjects will be followed until drop-out, death or End of Trial. Drop-out may be due to withdrawal of consent from further data collection or loss to follow-up. Subjects who drop-out or are alive at End of Trial will have their OS times censored at the time of last contact, as appropriate.

The analysis of the primary endpoint will use the stratified log-rank test in the ITT population. This test will provide the pivotal p-value summarizing the comparison of the two OS curves of AG-221 and CCRs. Subjects will be analyzed as they were randomized, regardless of the actual treatment received. The stratification used for the log-rank test will be the same stratification used for randomization. The corresponding stratified Cox proportional hazards regression model with treatment as the only term will be used to estimate the hazard ratio and a 95% confidence interval.

The assumption of proportional hazards will be tested by a time-dependent Cox model with the interaction of treatment and time. A significant interaction indicates that the proportional hazard assumption is violated. Under such circumstance, restricted mean survival time and piecewise Cox regression will be adopted to estimate treatment effect. Generalized Wilcoxon test will be utilized as a sensitivity analysis when treatment difference occurs early rather than late during the Follow-up period.

In order to assess the impact of subsequent enasidenib treatment in the CCR arm, sensitivity analyses of OS will be conducted following ICH E9 (R1) addendum, in which strategies to address intercurrent events are described. To be specific, Hypothetical Strategy, eg, regression-based imputation method (Luo, 2016) and Rank Preserve Structure Failure Time model (Robins, 1991), Principal Stratum Strategy, eg, Inverse Probability of Censoring Weighted method (Robins, 2000), and While on Treatment Strategy to censor subjects at the time of crossover will be adopted to provide supporting evidence when appropriate. In addition, to assess the impact of subsequent transplantation, a sensitivity analysis of OS will be conducted in which subjects who have subsequent transplantation will be censored at the time of transplantation after study treatments.

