### 11.2. Study Discontinuation

Discontinuation from study treatment should be considered distinct from discontinuation from the study. All subjects discontinued from study treatment for any reason other than withdrawal of consent for follow-up, death or lost to follow-up will be followed in the Follow-up Phase of the study (Section 6.3). Every attempt should be made to collect all data during the Follow-up Phase unless subjects discontinue from the study.

The following events are considered sufficient reasons for discontinuing a subject from the study:

- Screen failure
  - IDH2 mutation negative
  - Other

- Adverse event
- Withdrawal by subject from study
- Death
- Lost to follow-up
- Other (to be specified on the eCRF)

The reason for study discontinuation should be recorded in the eCRF and in the source documents.

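### Protocol 11.2 and SAP section 6 accept reasons for leaving the study that protocol 6.3 and 9.6.1 do not, so some OS follow-up could end early and be censored informatively

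*SAP*

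**What the plan says.** **The narrow rule.** Protocol 6.3 schedules survival contact every 4 weeks "until death, lost to follow-up, withdrawal of consent for further data collection, or the End of Trial, whichever occurs first". The survival footnote to protocol Table 3 and footnote kk in SAP 15.4 name the same four end points. Protocol 9.6.1 agrees for the primary analysis: "Drop-out may be due to withdrawal of consent from further data collection or loss to follow-up".

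**The wider lists.** Protocol 11.2 first separates stopping treatment from leaving the study. It sends everyone who stops treatment into follow-up unless they have died, are lost, or have withdrawn consent. It then says "The following events are considered sufficient reasons for discontinuing a subject from the study", and the list includes adverse event and an open Other. It also limits the data-collection duty: "Every attempt should be made to collect all data during the Follow-up Phase unless subjects discontinue from the study".

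SAP section 6 has one list for treatment and a second for the study: "Reasons for study discontinuation will be collected on the CRF and will be summarized for all randomized subjects", with a further summary for those entering follow-up. The second list adds progression, relapse, physician decision, pregnancy, protocol violation and "Transition to commercially available treatment". SAP section 13, on changes from the protocol, mentions only the transfusion-independence analysis.

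**The censoring rule.** SAP 10.2 censors subjects who are alive, or whose death status is unknown, at the last date known alive. It also plans a tabulation: "Reasons for censoring (e.g., lost to follow-up, withdrew consent, alive at data cut-off, Discontinuation due to other reasons"). The last of those reasons has no counterpart in protocol 9.6.1.

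**The concern.** OS is meant to count every death after randomization. Progression, relapse and toxicity are prognostic, and a move to commercial drug may differ between the arms. If a site closes a subject's study record for one of these reasons and nobody looks for vital status afterwards, OS is censored when the risk of death may be well above that of the subjects still followed. The log-rank test and Cox model assume that this does not happen.

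The nine numbered sensitivity analyses in SAP 10.2 cover the mITT population, transplantation and subsequent therapy. None addresses exit from the study for progression, relapse or adverse event. The RPSFT and imputation analyses also rely on survival observed after the switch.

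**Working it through.** **1. The lists side by side (randomized subjects).**

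| Reason | Protocol 6.3 / 9.6.1 | Protocol 11.2 | SAP 6 |
|---|---|---|---|
| Death | yes | yes | yes |
| Loss to follow-up | yes | yes | yes |
| Withdrawal | of consent to data collection | by subject, from study | by subject |
| End of Trial / sponsor termination | yes | not listed | yes |
| Adverse event | no | yes | yes |
| Other | no | yes | yes |
| Progression, relapse, physician decision, pregnancy, protocol violation, transition to commercial treatment | no | no | yes |

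The SAP list has 13 entries. Four match the narrow rule and one (screen failure) belongs before randomization. That leaves 13 − 4 − 1 = 8 with no counterpart in 6.3 or 9.6.1. Two of these eight, adverse event and Other, come from protocol 11.2 itself.

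**2. The plan's own design.** Inputs from protocol 9.3 and 9.8: medians 5.6 and 8 months, HR 5.6/8 = 0.70, two-sided alpha 0.05, 80% power, 250 deaths, 316 subjects, interim at 163 deaths.

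- Schoenfeld: 4 × (1.960 + 0.842)² / (ln 0.7)² = 31.40 / 0.1272 ≈ 247 deaths. Freedman's formula gives 253.
- With the interim at 163/250 = 0.652, the one-sided boundaries are 0.0055 and 0.0233, as stated, and power is 80.0%.
- Final HR boundary: exp(−2 × 1.99 / √250) = 0.7775, as stated.
- With the stated accrual, expected deaths at month 49 (42 + 7) are about 255 if the 9% drop-out is per year and about 250 if it is overall. The documents do not say which.

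The design reproduces.

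**3. What early exit could do.** The documents give no exit rates, so these are assumptions. Exit occurs at a uniform 40% to 90% of a subject's own survival time and no vital status is obtained afterwards. Exits come on top of independent drop-out of 9% per year. The model is exponential OS with 316 subjects and a cut-off at month 49. The test is an unstratified log-rank with one look at z = 1.99, over 1,500 runs. The Monte Carlo standard error of a percentage is at most √(0.25/1500) = 1.3 points.

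| Exit CCR / AG-221 | HR (true 0.70) | Rejection rate, true HR 0.70 | Deaths at month 49 | One-sided rejection, true HR 1.0 |
|---|---|---|---|---|
| 0 / 0 | 0.70 | 81% | 255 | 3% |
| 10% / 10% | 0.70 | 76% | 229 | 3% |
| 20% / 20% | 0.69 | 73% | 204 | 3% |
| 10% / 0 | 0.75 | 60% | 242 | 1% |
| 20% / 0 | 0.82 | 30% | 228 | 0% |
| 20% / 10% | 0.75 | 55% | 216 | 1% |
| 0 / 10% | 0.65 | 91% | 243 | 9% |
| 0 / 20% | 0.59 | 97% | 231 | 22% |

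The nominal one-sided level at the final look is 2.3%. The high rejection rates in the last two rows are bias, not real power.

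**4. If the analysis waits for 250 deaths.** With unlimited follow-up and 9% annual drop-out, 316 subjects yield about 293 deaths. Equal exit of 10% leaves 0.9 × 293 = 264, so 250 is reached, but later. Equal exit of 20% leaves 0.8 × 293 ≈ 235, so 250 is not reached without more subjects. With no other drop-out, equal exit of 12% at 70% of survival time moves the 250th death from about month 45 to about month 53, with power near 81%.

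**The case against.** A reader might infer that the SAP lets a site end survival follow-up at progression, relapse or a switch to commercial drug. The documents do not support that. SAP section 6 says how CRF categories will be summarized, and sites work to the protocol. Protocol 3.1.3, 6.3 and 11.2, and SAP 4.1, all require survival follow-up after treatment stops unless consent is withdrawn, with 11.2 also excepting death and loss to follow-up. Progression, relapse and transition are not study-exit reasons in 11.2. Only adverse event and Other are.

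Nor is OS automatically censored when a record is closed. SAP 10.2 has no rule that censors at study discontinuation, and its description of subjects still in the study mentions only loss to follow-up and withdrawn consent. Protocol 6.3 allows vital status to be found from records, including public ones, and a death found that way counts. The category for other reasons sits in a descriptive table, which would help expose the problem.

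It would also be wrong to say that every crossover analysis needs deaths after the switch. The IPCW analysis of off-protocol AG-221 censors at the switch. It needs the switch date, not what follows.

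All of this stands and narrows the point. It does not remove the conflict. Protocol 11.2 itself permits exit for two reasons that 6.3 and 9.6.1 exclude, and relaxes data collection afterwards. The CRF list is longer still. Neither document commits to finding vital status for subjects closed this way.

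**Conclusion.** The contradiction in the stated rules is real and concerns what ends follow-up for the primary endpoint. The harm is conditional: it needs subjects closed for one of the extra reasons, without withdrawn consent, whose vital status is not then obtained.

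Neither size nor direction can be fixed from the documents. A reader might infer that deaths are lost mainly from the CCR arm, because the amendment rationale expects some CCR subjects to take commercial AG-221. But the transition category in SAP section 6 names no arm and no drug, and an AG-221 subject moving to commercial supply fits it equally well. More exit in CCR moves the HR toward 1, against AG-221. More exit in AG-221 favours AG-221 and can inflate false positives, to about 9% one-sided at 10% exit under the assumptions above. Equal exit leaves the HR almost unchanged and costs deaths or time. Swapping the arms reverses the sign, so no single HR shift should be quoted as the expected effect.

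**What to change.** Reconcile protocol 11.2 and SAP section 6 with protocol 6.3 and 9.6.1. For randomized subjects, only death, loss to follow-up, withdrawal of consent to data collection, or End of Trial/sponsor termination should end survival follow-up. The other eight reasons should be recorded as treatment discontinuation only. All eight are already on the SAP treatment-discontinuation list, so no new category is needed. Record the change in SAP section 13.

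Before lock, obtain vital status at data cut-off for every subject closed without withdrawing consent, by the record or public-record review that 6.3 already permits, and use it in OS. Report OS censoring by reason and arm. Add a sensitivity analysis for exits for other reasons, for example one that raises the assumed hazard after exit separately in each arm until the conclusion changes.

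The cost is a wording amendment (with written IRB/EC approval under protocol 13.5 unless it is administrative), a SAP revision, a CRF completion note and one vital-status check. It needs no new visits or subjects.
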